5.0 Data Management

All physiological data will be stored in password-protected computers in the PI's laboratory that is always locked with a touchpad keyless entry system. Data will be backed up on UCSF's HIPPA-compliant server. In publications or presentations of the data, data will be grouped by case number in chronological order with no name identification. All DBS patients at our center routinely undergo videotaping and sign a separate consent to be videotaped. When presenting videotape data at scientific conferences, we will utilize only videos from patients who have consented to have their videos shown. De-identified electrophysiological data may be shared with other researchers at other institutions.

Clinical data (baseline and follow up rating scales) will be entered into a customized, password-protected encrypted web-based database (LAVA). This resides on a server at UCSF and is managed by the Department of Neurology, with backup support by the information technology service at UCSF. The database can be accessed by a licensed user from a secure Internet server at UCSF but is protected by firewalls from networks outside of our institution.

Any on-line or text messaging data collected will not include personal identifiers.

6.0 Statistical Methods and Data Analysis

Ratings of pain will be measured by visual analog scales for pain as well as unpleasantness of pain sensation (i.e. “how much pain are you in right now?” and “how much is the pain bothering you right now?”). Patient reports of sensory and pain detection using the Quantitative sensory testing (QST) with the Medoc device will also be used, with and without stimulation.

In Phase 2, patients will serve as their own controls in a single-blinded phase (6-months in duration) in which placebo versus active open-loop stimulation is used. During this 6-month period, four sham and four active stimulation periods will occur in a random, blinded assignment. During the 8 in-clinic visits, the threshold for sensory and pain detection with the Medoc device will be used and scores will be compared for each patient during sham versus active stimulation periods in one-sample, two-tailed t-test. The 10 patients’ sham versus stimulation scores will also be used in group analysis to test the effects of open-loop and closed-loop stimulation.

In Phase 2, the visual analog scale scores recorded during the at-home recording sessions for various activities will be compared for each patient [(see Figure 3; 168 scores for sham sessions and 168 scores for active stimulation sessions, per patient); (i.e. 3 times per week for 4 activities and 2 times per week for at least 1 painful activity, for at least 14 VAS scores per week; 24 weeks total with 3 weeks per session-sham or stimulation, 8 sessions total, 4 sham sessions and 4 stimulation sessions)].

Multiple regression analysis of all patients will also be used to test for effects of stimulation on various activities, time of day, stimulation effects over time in trial and potential differences in stimulation effects on pain etiologies (i.e. spinal cord injury versus phantom limb versus post-stroke).

Phase 1 (no-intervention) VAS scores will be compared to Phase 2 (sham controlled and active stimulation) VAS scores.

In Phase 3, patients will serve as their own controls in a single-blinded phase (12-months in duration) in which closed-loop versus active open-loop stimulation is used. During this 12-month period, ~four sham and ~four active stimulation periods will occur in a random, blinded assignment. During the ~8-9 in-clinic visits, the threshold for sensory and pain detection with the Medoc device will be used and scores will be compared for each patient during sham versus active stimulation periods in one-sample, two-tailed t-test. The 10 patients’ sham versus stimulation scores will also be used in group analysis to test the effects of open-loop and closed-loop stimulation.

In Phase 3, the visual analog scale scores recorded during the at-home recording sessions for various activities will be compared for each patient [(see Figure 3; ~364 scores for sham sessions and ~364 scores for active stimulation sessions, per patient); (i.e. ~3 times per week for 4 activities and 2 times per week for at least 1 painful activity, for at least ~14 VAS scores per week; ~52 weeks total with 6 weeks per session-sham or stimulation, ~8 sessions total, 4 sham sessions and 4 stimulation sessions)].

Multiple regression analysis of all patients will also be used to test for effects of stimulation on various activities, time of day, stimulation effects over time in trial and potential differences in stimulation effects on pain etiologies (i.e. spinal cord injury versus phantom limb versus post-stroke).

Phase 1 (no-intervention) and Phase 2 (sham controlled and open-loop stimulation) VAS scores will be compared to Phase 3 (open-loop stimulation and closed-loop) VAS scores.

LFP data will be analyzed using wide spectrum power-spectral analysis as well as using specific frequency domain for mean log power (i.e. in the delta, theta, alpha, beta, gamma bands). We will also examine coherence and cross-frequency coupling between the channels [145-147]. Using a repeated measures ANOVA statistical analysis, summary statistics for power in relevant frequency bands, pain-related power changes, and indices of phase-amplitude coupling will be compared at different time points, different DBS conditions (on and off), possible medication states (on and off) and different pain states. Although the sample size is small, we will assess the correlation between pain and non-pain states with brain physiology measures, and clinical instruments used to measure pain relief produced by DBS. Additionally, bootstrapping statistical applications (i.e. a Monte Carlo algorithm) and general linear mixed models can be utilized to investigate potential statistical effects, given the small sample size.

Neural activity will be compared during pain states, activity states, medication states, etc. for Phase 1 (no-intervention), as well as Phase 2 (sham controlled and open-loop stimulation) and Phase 3 (open-loop stimulation and closed-loop stimulation).

Sample size calculation: This is a pilot study consisting of existing chronic brain recording technology. The goals are to provide pain relief strategies using the Activa PC+S neural interface, as well as assess feasibility and to collect data that will be used to inform treatment plans using DBS mechanisms. Thus, there is no formal sample size calculation. However, the study is designed such that patients will serve as their own controls in a blinded, placebo versus active open-loop stimulation design, with multiple periods of placebo versus active stimulation. Patients will also serve as their own controls in open-loop versus closed-loop stimulation, in a randomly assigned, blinded, multiple 6-week time periods of open-loop versus closed-loop stimulation. At-home recording sessions will also be utilized to increase the number of testing samples per patient over the trial. In this manner, the statistical power is increased to show treatment efficacy in either of these phases.

Criteria for study success that would justify a larger subsequent trial: This study will be considered to justify a larger subsequent trial if we can demonstrate that:

- 1) Chronic LFP recordings are of adequate quality to assess the LFP signatures of elevated pain.
- 2) No permanent serious adverse events occur (such as trauma with long-term motor deficit).
- 3) Using the Nexus System, therapeutic benefit from stimulation can be demonstrated (i.e. cessation of a pain episode or decreased pain symptoms).

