	
 • MRI (done within one year of the first visit) with significant abnormalities other than those associated with the neurological disorder causing chronic pain. • Implantable hardware not compatible with MRI or with the study. • Inability to comply with study follow-up visits • Previous ablative intracranial surgery for the management of the thalamic pain syndrome. • Previously implanted with deep brain stimulation system or any previously implanted device treatment involving brain stimulation • Major neurological disorder other than the one that led to the chronic pain including epilepsy, neurodegenerative condition or any history of seizure • Requires diathermy, electroconvulsive therapy (ECT) or transcranial magnetic stimulation (TMS) to treat a chronic condition • Has an implanted electronic device such as a neurostimulator, cardiac pacemaker or medication pump • Allergies or known hypersensitivity to materials in the Activa PC+S system (i.e. titanium, polyurethane, silicone, polyetherimide, stainless steel). • Pregnancy or lack of regular use of contraceptives. Patients who become pregnant after enrollment may be excluded from the study. Patients who become pregnant prior to the surgical implantation of the DBS systems will be excluded from the study. • Patients may be excluded from enrollment due to a condition that, in the judgment of the PI, significantly increases risk or reduces significantly the likelihood of benefit from DBS.
Sample Size	10 patients
Efficacy Assessments	Primary Endpoints 
 • Pain intensity / relief visual analog scale • Thermal pain threshold testing with QST Secondary Endpoints 
 • Neuropathic Pain Questionnaire • NIH PROMIS Global health and physical function scales • SF-36

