A predictive biomarker of pain will be discovered in phase 1 from data collected with at-home and in-clinic recording sessions. This biomarker discovery will be implemented in Phase 2. In phase 1, if data of sufficiently high quality is collected before the 6-month phase period ends, and a predictive biomarker is found before the 6-month phase period ends, the patient can accelerate to the next phases of the study to help ensure a rapid positive clinical outcome.

Phase 2

In the first two weeks of Phase 2, patients will be seen daily for up to two weeks to optimize DBS parameters (visits 11-24), based on biomarker discovery from Phase 1. EEG may be used during this phase for safety, to ensure that subclinical seizure activity is not present during stimulation. If data-collection during the initial two-week period is curtailed for any reason, additional DBS optimization visits may be scheduled so as to sufficiently optimize the biomarker and stimulation settings to enable closed-loop stimulation.

Patients will then have closed-loop stimulation enabled for at-home stimulation, with follow-up clinic visits scheduled every 3 weeks. Stimulation will be enabled or disabled in an ON/OFF state with patient blinded to stimulation status to test for potential placebo / sham effects. In addition to at-home reporting (similar to Phase 1), efficacy of stimulation will be tested every three weeks in-clinic. Additional in-clinic testing of stimulation-related analgesia efficacy and mechanism of action will be done using acute administration of intranasal (4mg/0.1ml, up to two doses), intramuscular (0.4mg/1ml) or IV naloxone (0.4mg/1ml), or saline as control. Study team will assist in administering naloxone before and during analgesic stimulation ON/OFF. Patients and study team will be blinded to what is being provided. Patients who are participating in pain management using opioids will be excluded from performing this study procedure. Phase 2 will last approximately 6 months in duration, time period based on previous unpublished observations in human Parkinson's

patients from our group [143] and published non-human primate observations [58]. Phase 2 in-clinic visits occurring every 3 weeks will test the following:

- 1) VAS pain, VAS unpleasantness, C-SSRS, BDI/BAI, Neuropathic Pain Scale, NIH PROMIS Global health and physical function scales, and SF-36
- 2) Baseline LFP
- 3) Stimulation off + QST (no pain medication)
- 4) Stimulation on + QST (no pain medication)

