loop stimulation will test a strategy for automated control of DBS settings with aberrant signaling in pain states triggering stimulation. To test stimulation strategies, at the start of a session in phase 2, LFP data will be collected in elevated pain states. These data will be streamed using the Nexus System in conjunction with software from the Nexus programming interface. The Nexus System provides a conduit between Activa PC+S and a computer and can transfer stimulation update commands to Activa PC+S. During the streaming procedure stimulation settings may be automatically, iteratively, adjusted based on markers of oscillatory activity such as cortical phase-amplitude coupling (PAC) or beta band power. These adjustments will always remain within allowable settings pre-programmed by a clinician using standard procedures (i.e. using the Medtronic 8840 programmer).

Phase 2 will test the effectiveness of closed-loop stimulation in comparison to no-stimulation. Daily visits will take place for the first 2 weeks of phase 2, and regular clinic visits occurring every three weeks during Phase 2 (~ 6 months in duration).

Stimulation states for Activa PC+S brain data collection: In phase 1, the optimal times of day that patients are most likely in a pain state will be assessed and used to schedule appointments in the outpatient clinic for phase 2 (i.e., we will schedule phase 2 recording and stimulation sessions for each patient to coincide with optimal time of pain states, as determined by patterns of maximum and predictable pain states from phase 1). In Phase 2, for the first recording session that includes a DBS-on condition, (after the initial up to 2 week period of optimizing stimulation parameters), the following data will be recorded:

- 1) VAS pain, VAS unpleasantness, C-SSRS, BDI/BAI, Neuropathic Pain Questionnaire, NIH PROMIS Global health and physical function scales and SF-36
- 2) Baseline LFP
- 3) Stimulation off + QST (no pain medication)
- 4) Stimulation on + QST
- 5) Wash-out, stimulation off period
- 6) LFP recording after painful activity
- 7) Recording after pain medication
- 8) EEG activity

Visits are as follows:

13. Visit 11-24: Every day for 2 weeks, stimulation optimizing:

- Clinical only: Daily visits 11-24 DBS programming initial and revisits if needed. Full history and physical exams to document changes that occur during closed loop stimulation.
- Research: C-SSRS, BDI/BAI visits 11, 18 and 24.

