14. Visits 25-31: every 3 weeks for closed loop / placebo randomization:

- Clinical: visit 28 only; History and Physical for stability
- Research: visits 25-31: Activa Data collection + QST:
- Quantitative sensory testing (QST) with the Medoc device. Using cold and heat, we will test sensory perception and pain thresholds 3 times each in the aspect of both hands (contra and ipsi lateral to pain). The device will slowly increase/ decrease temperature until the patient reports sensation (1st endpoint) and then pain (2nd endpoint) which will be recorded. Heat and cold perception and pain thresholds will be tested, with the patient record VAS for pain threshold on each trial. Three consecutive trials will be conducted in each session to establish reliability. LFP recordings will be recorded during the QST sessions with clinician initiated recording. LFP recordings will also be recorded during pre-identified painful activities or

movement and after painful activity with VAS scores recorded during these times as well.

- Patients will be asked to avoid pain medication two hours prior to their appointments. Post-testing, patients will then take medications and 2-minutes of recording will be obtained 15-minutes after pain medication is given.
- Baseline LFP recordings will also be taken from ~2 minutes.
- Stimulation off + QST (no pain medication)
- Stimulation on + QST
- Wash-out, stimulation off period
- LFP recording after painful activity
- Recording after pain medication
- C-SSRS/BDI/BAI/ NIH PROMIS /NPQ/physical function scales and SF-36

Phase 2 will last approximately 6 months in duration, time period based on previous unpublished observations in human Parkinson's patients from our group [143] and published non-human primate observations [58], visits 11-34, if needed)

Phase 2 will test the effectiveness of closed-loop stimulation in comparison to no-stimulation.

In phase 3, the effectiveness of closed-loop stimulation will be tested in comparison to open-loop stimulation settings.

Phase 3

In phase 3, patients will continue with at-home stimulation with either personalized closed-loop or traditional open-loop stimulation strategies their implanted system. Patients will be blinded to the stimulation strategy in which they are assigned. Assignment of open-loop or closed-loop will be randomized and occur in 6-week time periods, with each patient serving as his or her control as to which stimulation treatment is more effective.

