4.0 Clinical Measurements

Primary

Clinical ratings of pain will be measured by visual analog scales for pain as well as unpleasantness of pain sensation (i.e. “how much pain are you in right now?” and “how much is the pain bothering you right now?”). Patient reports of sensory and pain detection using the Quantitative sensory testing (QST) with the Medoc device will also be used, with and without stimulation.

Physiological measurements related to neural oscillatory activity during various triggered neural recordings with various pain states, activity states, medication states, etc. (~14 recordings per week at home, ~6-8 recordings per in-clinic visit,) will include: wide spectrum power-spectral analysis as well as using specific frequency domain for mean log power (i.e. in the delta, theta, alpha, beta, gamma bands), pain-related changes in broad spectrum power density, and coupling between the phase of low frequency rhythms and broadband gamma amplitude (phase-amplitude coupling, abbreviated PAC) [145-147].

Clinical measures and physiological measurements will be collected and recorded by members of the research and clinical team, as well as from at-home data collection sessions.

Secondary

Measures from Neuropathic Pain Questionnaire, Beck Depression and Anxiety, NIH PROMIS Global health and physical function scales and SF-36 will also be compared from pre-intervention to post Phase 1, phase 2 and phase 3 time points.

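### Section 6.0 misstates the QST analysis: Phase 3 is tested as sham versus active although it compares open-loop with closed-loop, the Phase 2 visit count and stimulation mode conflict with the schedule, and the QST battery analysed is not named

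*Combined protocol and SAP*

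**What the plan says.** The synopsis lists "Thermal pain threshold testing with QST" among the primary endpoints. Section 4.0 adds that "Quantitative sensory testing (QST) with the Medoc device will also be used, with and without stimulation".

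**Section 6.0, Phase 2.** Placebo is compared with active open-loop stimulation over six months, in four sham and four active periods in random order. QST is taken at 8 clinic visits, and "scores will be compared for each patient during sham versus active stimulation periods in one-sample, two-tailed t-test". A group analysis of the ten patients' sham and stimulation scores follows.

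**Section 6.0, Phase 3.** The paragraph opens by describing closed-loop against open-loop stimulation over 12 months. It then specifies about four sham and about four active periods, about 8 to 9 visits, and the same t-test and group analysis.

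**Sections 1.0 and 3.0, Phase 2.** Closed-loop stimulation is enabled at home, and "Stimulation will be enabled or disabled in an ON/OFF state with patient blinded to stimulation status". Both sections state that the phase compares closed-loop stimulation with none. Section 3.0 and the Protocol Chart place the QST visits at 25 to 31.

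**Visit lists.** Every Phase 2 and Phase 3 list has two QST batteries. Section 1.0 lists an OFF battery and then "Stimulation on + QST (no pain medication". Section 3.0, for visits 25 to 31, lists "Stimulation off + QST (no pain medication", an ON battery, and then "Wash-out, stimulation off period". Section 3.0 introduces its Phase 2 list as being "for the first recording session that includes a DBS-on condition".

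**The concern.** The trial has no formal sample size calculation, so the analysis text is the only definition of what a QST result would mean. That text conflicts with the design in three places and leaves a fourth open.

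In Phase 3, a literal reading compares two conditions that the phase does not randomise, while the comparison that it does randomise has no stated QST test. Phase 3 is meant to show which strategy is better for each patient, so the omission reaches a stated aim. In Phase 2, the number of observations behind the per-patient test and the mode of stimulation being tested both depend on which section is read. In both phases, the choice of battery could be made after the data are seen, and the candidate choices answer different questions.

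**Working it through.** **(a) Phase 3 contrast.** Places that describe the Phase 3 assignment:
- Section 1.0 and Section 3.0 (Phase 3, and again under Nexus System Study): open-loop or closed-loop, randomised in 6-week periods, each patient as own control.
- Protocol Chart: open versus closed.
- Section 6.0, opening of the Phase 3 paragraph and the sample size paragraph: open-loop versus closed-loop.
- Section 6.0, remainder of the Phase 3 paragraph: sham versus active, for the periods, the QST test and the at-home VAS counts.

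Only the last differs. The period count itself fits an open/closed design: 52 / 6 = 8.7, in line with about 8 to 9 visits. The label is wrong rather than the layout.

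**(b) Phase 2 visits.** Section 6.0 agrees with itself: 24 weeks / 3 weeks per period = 8 periods, 4 sham and 4 active. Its VAS count also reproduces: 3 × 4 + 2 × 1 = 14 scores per week, and 14 × 24 / 2 = 168 per condition.

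The schedule gives 31 − 25 + 1 = 7 visits, and the Protocol Chart also says 7. With one QST visit per period, 8 − 7 = 1 period has no visit, and the comparison is at best 4 against 3. A one-sample test of sham against active needs paired differences. Four pairs give 4 − 1 = 3 degrees of freedom. Seven visits give at most 3 pairs, 3 − 1 = 2 degrees of freedom, with one visit unused.

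Elsewhere, Section 3.0 allows up to ten additional visits and gives the range for Phase 2 once as 11 to 31 and once as 11 to 34, each where needed. The second range runs into Phase 3, which starts at visit 32.

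**(c) Phase 2 mode.** Open-loop: Section 6.0 in the Phase 2 paragraph, the cross-phase VAS comparison, the neural-activity paragraph and the sample size paragraph. Closed-loop: Section 1.0 (Phase 2), Section 3.0 (Phase 2, the heading for visits 25 to 31, and Nexus System Study) and the Protocol Chart.

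**(d) Which battery.** Let A be the acute effect of stimulation during testing, C the effect carried into the visit from an active home period, and O a constant shift from being tested second. Assume that these add and that OFF is tested before ON. The expected active-minus-sham difference is:
- OFF vs OFF: C − 0 = C.
- ON vs ON, ON delivered at every visit: (C + A + O) − (A + O) = C.
- ON vs ON, ON not delivered at sham-period visits: (C + A + O) − O = C + A.
- Mean of both batteries: C if ON is delivered at every visit, C + A/2 if not at sham-period visits.
- ON at active visits vs OFF at sham visits: C + A + O.

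For illustration, with A = 1 SD and C = O = 0, these are 0, 0, 1, 0 or 0.5, and 1 SD. Section 6.0 does not choose among them.

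**The case against.** **Pilot status and clear intent.** This is a ten-patient feasibility study, and its criteria for a larger trial do not mention QST. The Phase 3 label looks like text carried over from Phase 2, and the sample size paragraph shows what was meant. That is fair and limits the severity. It also means that the correction is uncontroversial, and the sentence that specifies the primary-endpoint test is still wrong.

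**Phase 3 does have an off state.** The last item of the Phase 3 list in Section 1.0 allows stimulation to be turned off for up to two months. It is described as a wash-out, however, and nothing makes it one of about four randomised sham periods.

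**An eighth visit is possible.** Up to ten additional visits are allowed, and visit 32 might serve to close the last Phase 2 period. Neither is stated as the plan, and the chart assigns visit 32 to Phase 3.

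**The battery question is missing detail.** Largely so. Taken literally, the single list for visits 25 to 31 has stimulation on for the ON battery at every visit. The chart's reference to VAS before and during stimulation at those visits points the same way. The reference to a first session that includes a DBS-on condition may suggest that some sessions lack one. The text does not settle it.

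**A stronger reading that does not hold.** Since OFF is always listed before ON, a reader might infer that the planned QST test is biased by test order. The documents do not support that. The only QST test in Section 6.0 is between periods, and a constant order shift cancels in the like-for-like contrasts shown in (d). On and off are a named factor only for the LFP analysis. The lists are also not reliably chronological: for visits 25 to 31, the post-medication recording appears before the baseline recording and the OFF battery, and again at the end. Order would matter only for a contrast that sets ON against OFF, and only if list order is test order. Nor do the documents justify requiring balanced order: testing ON first risks carry-over into OFF, and the wash-out length is not stated.

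**Conclusion.** The point holds and should be fixed. The Phase 3 QST test as written does not address the Phase 3 question. The scheduled Phase 2 visits number 7, against the 8 that Section 6.0 relies on. The Phase 2 stimulation mode conflicts between Section 6.0 and Sections 1.0 and 3.0. The primary QST contrast is undefined, and if ON is delivered at every visit, comparing OFF with OFF or ON with ON between periods excludes the acute effect.

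The four-against-three count assumes one QST visit per period and no added visit. The range from none to all of the acute effect rests on additive effects. The 1 SD value is illustrative, since the documents give no QST effect or SD. No false-positive rate is claimed for the planned test. The Phase 2 at-home VAS count is not affected by the visit or battery questions, but it shares the Phase 2 mode conflict, and the Phase 3 VAS text carries the same sham label.

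**What to change.** 1. In the Phase 3 paragraph of Section 6.0, replace the sham-versus-active QST contrast with open-loop versus closed-loop periods, and correct the same label in the group analysis and VAS counts.
2. Reconcile 8 against 7 Phase 2 QST visits across Section 6.0, Section 3.0 and the Protocol Chart. Restate how many sham and active QST observations each patient contributes and how the one-sample differences are formed.
3. Reconcile the Phase 2 stimulation mode across Sections 1.0, 3.0 and 6.0.
4. Before data are reviewed, name one primary QST contrast and state whether stimulation is delivered during the ON battery at sham-period visits.
5. If a within-visit ON-minus-OFF contrast is to be reported, state the test order and the wash-out, and note that under a fixed OFF-then-ON order it cannot be separated from order effects.
6. As minor wording, reconcile the task items in Section 1.0 that are listed twice as stimulation off, and the no-pain-medication label, which is on both batteries in the Phase 2 list of Section 1.0 but only on OFF in the other lists.

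The cost is protocol and SAP wording. No patients are added. A visit would be added only if item 2 is settled by scheduling an eighth.

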Quantitative sensory testing (QST) with the Medoc device. Using cold and heat, we will test sensory perception and pain thresholds 3 times each in the aspect of both hands (contra and ipsi lateral to pain). The device will slowly increase/ decrease temperature until the patient reports sensation (1st endpoint) and then pain (2nd endpoint) which will be recorded. Heat and cold perception and pain thresholds will be tested, with the patient record VAS for pain threshold on each trial. Three consecutive trials will be conducted in each session to establish reliability. LFP recordings will be recorded during the QST sessions with clinician-initiated recording. A computerized cognitive-attention task will be performed. We will test patient reaction time and short-term memory recall using a computerized task, requiring patients to respond to tasks by pressing a keyboard key and verbally recalling words during the memory task. Three consecutive trials will be conducted within a single session with the task order shuffled to establish test reliability. LFP recordings will be recorded during the cognitive-attention task sessions with clinician-initiated recordings. We will also conduct an anticipatory anxiety task where participants will be provided with a non-painful, random buzzing stimulation on the finger paired with a continuous auditory cue indicating which period of time will contain random irritating stimulation. Finger stimulation using a BIOPAC stimulation will be titrated up to a non-painful, highly irritating voltage before each task session. We will be collecting LFP recordings throughout this task to record pain anticipation signals. LFP recordings will also be recorded during pre-identified painful activities or movement and after painful activity with VAS scores recorded during these times as well. Patients will be asked to avoid pain medication two hours prior to their appointments. Post-testing, patients will then take medications and 2-minutes of recording will be obtained 15-minutes after pain medication is given. We may also use electroencephalography (EEG) to record brain data during some clinic visits to support biomarker identification.

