- 14) Closed-loop DBS being turned to open-loop stimulation setting, previous open-loop stimulation being turned to closed-loop DBS setting, randomized, or turning stimulation off for a wash-out period of up to 2-months.

Phase 3 will inform the research team as to whether open-loop or closed-loop stimulation is most effective on a patient-by-patient basis.

At the end of the study, patients will have the option for 1) continued active closed-loop or open-loop stimulation with the current implanted device, with in-clinic appointments, 2) discontinuing stimulation with the device turned off or 3) having the device removed.

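### The only test named for the QST primary endpoint, a per-patient one-sample t-test, does not fit the sham-versus-active period comparison, and the planned group analysis has no method

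*Combined protocol and SAP*

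**What the plan says.** The Efficacy Assessments row of the synopsis lists "Thermal pain threshold testing with QST" among the primary endpoints. Under Phase 2, Section 6.0 says that "four sham and four active stimulation periods will occur in a random, blinded assignment". It counts eight clinic visits with QST in that phase. The test itself is given in these words: "scores will be compared for each patient during sham versus active stimulation periods in one-sample, two-tailed t-test". The Phase 3 paragraph of Section 6.0 repeats the same comparison and test, although it introduces that phase as closed-loop against open-loop.

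Both paragraphs add a group analysis of the 10 patients' scores, with no test or model named. No alpha is stated. Later in Section 6.0, in the paragraph on LFP data, the plan says that "bootstrapping statistical applications (i.e. a Monte Carlo algorithm) and general linear mixed models can be utilized". That sentence is optional in tone and is not tied to QST.

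On measurement, Section 1.0 says "we will test sensory perception and pain thresholds 3 times each in the aspect of both hands", for both heat and cold. The visit lists in Sections 1.0 and 3.0 include QST with stimulation off and QST with stimulation on at the same visit. Section 3.0 and the Protocol Chart schedule the Phase 2 QST visits as visits 25 to 31, which is seven visits, not eight. Section 1.0 says that Phase 3 will show "whether open-loop or closed-loop stimulation is most effective on a patient-by-patient basis".

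**The concern.** A one-sample t-test compares one set of values with a fixed number. Here each patient supplies two sets, and both carry sampling error. The SAP does not say whether the single sample is the active scores set against the sham mean, differences between periods, or differences within a visit. These choices have different error rates, different power and, in one case, a different meaning. An analyst would have to choose after the data are in.

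This is one of two primary endpoints, and no other QST test is named. In Phase 3 the stated comparison, sham against active, is not the one that the phase is designed to make.

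**Working it through.** **Inputs from the documents.** Section 6.0 gives 24 weeks in 3-week periods: 24 / 3 = 8 periods, four sham and four active, which agrees with its own count. Section 3.0 gives visits 25 to 31, which is 7. There are 10 patients.

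**Assumptions, because the documents give no figures.** Two-sided alpha of 0.05; independent, normal visit-level errors with the same SD, σ; true effect d in units of σ.

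**Reading A: active scores against the sham mean as a constant.**
- The statistic is (active mean − sham mean) / (s/√4), referred to t with 3 df and critical value 3.182.
- The numerator has variance σ²(1/4 + 1/4) = σ²/2. The test allows for σ²/4, so the statistic is too large by √2.
- Error rate = P(|t₃| > 3.182/√2) = P(|t₃| > 2.250) = 0.110. A simulation of 400,000 patients gave 0.109.
- With unequal counts the factor is √(1 + n_active/n_sham). For 4 active and 3 sham visits: P(|t₃| > 3.182/1.528) = 0.129. For 3 active and 4 sham: P(|t₂| > 4.303/1.323) = 0.083.
- For one threshold in one phase, the chance of at least one false positive among 10 patients is 1 − 0.89¹⁰ = 69%, against 1 − 0.95¹⁰ = 40% at the nominal level.

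**Reading B: four period differences.**
- Four active and four sham values can be matched in 4! = 24 ways. All give the same mean difference, but the SD of the differences, and so the p-value, depends on the matching. The plan specifies none.
- For a matching fixed in advance, the error is 5% (simulation 4.97%). The noncentrality is d/√(2/4), with 3 df.
- A two-sample test has the same noncentrality, d/√(1/4 + 1/4), but 6 df.

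| True effect | Four differences, 3 df | Two-sample 4 v 4, 6 df |
|---|---|---|
| 0.5 SD | 8% | 9% |
| 1 SD | 17% | 22% |
| 2 SD | 49% | 66% |
| Effect for 80% power | 3.0 SD | 2.4 SD |

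Arbitrary pairing therefore loses some power, but the two-sample test is weak as well. The main limit is 4 v 4 visits.

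**Reading C: off/on differences within a visit.** Eight differences, 7 df, noncentrality d/√(2/8). Power is 41% at 1 SD and 93% at 2 SD if the two readings are uncorrelated.

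**Group analysis.** Each patient's mean difference has error variance 0.5σ². Let τ be the SD of true effects between patients, in units of σ. The noncentrality is d/√((0.5 + τ²)/10), with 9 df. At d = 1, power is 98%, 90% and 63% for τ = 0, 0.5 and 1. At d = 0.5 it is 51%, 37% and 21%.

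**The case against.** The strongest reply is that a one-sample t-test on differences is a paired t-test, is valid, and keeps its 5%. That is correct. A reader might infer that the named test cannot compare sham with active at all; the documents do not support that. The fault is that no pairs of periods are defined and random ordering supplies none.

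A second reply is that natural pairs do exist, because QST is done with stimulation off and on at each visit. This reading is more powerful, but it is a different contrast from the periods that Section 6.0 names. The visit lists put off before on and state no counterbalancing, so condition may be mixed with test order. In Phase 3 an off/on difference does not compare open-loop with closed-loop.

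A third reply is that power depends on quantities that the documents do not give. This stands. If paired periods were correlated at 0.5 or 0.8, power on four differences at 2 SD would be 76% or 98%. A patient's stable level creates no such correlation within that patient, so independence is a reasonable default, but it remains an assumption. To say that the test has almost no power would go too far.

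It is also fair that a group analysis is already planned, that this is a pilot with no formal sample size, and that none of the stated success criteria calls for a QST p-value.

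**Conclusion.** The point holds as a mismatch between the named test and the data, on a primary endpoint. With the sham mean held fixed, the error is about 11% instead of 5% (8.3% or 12.9% with seven visits). With four arbitrary differences the error is correct, but power falls below that of a two-sample test: 17% v 22% at 1 SD, 49% v 66% at 2 SD. These figures rest on alpha of 0.05 and on independent, normal visit errors with equal variance. The effect sizes are assumed.

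The gap at group level may matter more. The group analysis is the one with useful power at 1 SD, yet it has no method. In Phase 3 the stated contrast is also the wrong one.

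Three stronger inferences are not supported:
- That the plan relies on a faulty bootstrap. The sentence sits in the LFP paragraph, names no type of interval and also offers mixed models.
- That every QST threshold counts as a primary test. The endpoint is the pain threshold, so sensation thresholds fall outside it.
- That the Phase 3 patient-by-patient conclusion hangs on a QST significance test. That statement names neither QST nor a test.

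This should be fixed before analysis. It does not undermine the study, because the planned data can support a sound group analysis.

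**What to change.** In both the Phase 2 and the Phase 3 paragraphs of Section 6.0, replace the one-sample t-test as follows.

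1. Average the three trials at each visit. State which of the visit's off and on readings represents the period, and how the heat and cold pain thresholds on the two hands are ranked or combined.
2. Make the group analysis the main QST analysis, for pain thresholds. Fit one mixed model per phase, with condition and visit number as fixed effects, a random patient intercept, a random patient-by-condition effect, and small-sample degrees of freedom. The contrast is active against sham in Phase 2 and closed-loop against open-loop in Phase 3.
3. Confirm the group result by re-randomising period labels within patients under the allocation scheme actually used, and state that scheme.
4. Report per-patient effects as estimates with intervals, or with a two-sample or within-patient permutation test labelled exploratory. The scheme matters here: if any 4 of 8 periods may be active there are 70 arrangements and the smallest two-sided p-value is 2/70 = 0.029. If periods are randomised in pairs there are 2⁴ = 16, and the smallest is 2/16 = 0.125.
5. Reconcile the eight Phase 2 visits in Section 6.0 with visits 25 to 31 in Section 3.0 and the Protocol Chart.

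The cost is SAP wording and modest programming, with no new data. Per-patient p-values lose any confirmatory status.
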